4.4 CONCOMITANT THERAPY

Concomitant therapy includes any background drug or substance (e.g., prescription drugs, over-the-counter drugs, herbal or homeopathic remedies, nutritional supplements) used by a patient from the time the patient is screened in the study until study completion. This includes any preventative vaccines (e.g., tetanus or flu vaccines) that the patient may receive during the course of this study. All such medications should be reported to the investigator and recorded on the Concomitant Medications eCRF. It should be noted that live or attenuated vaccines (e.g., certain formulations of influenza vaccines) are not permitted. Additional use of immunosuppressive medications, cell-depleting agents, or other standard-of-care therapies per best medical judgment must be reported as concomitant medications.

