4.4.2 Additional Permitted Therapy and Procedures

Patients who use oral contraceptives, hormone-replacement therapy, or other maintenance therapy should continue their use.

Patients not already taking vitamin D (400 IU/day) and calcium supplements (1200 mg/day calcium citrate or 1500 mg/day calcium carbonate) may start these supplements at study initiation. *Pneumocystis jirovecii* pneumonia prophylaxis may be performed according to local clinical practice guidelines and investigator judgment.

From Week 12 through Week 52, an additional provision is made for patients who would otherwise be withdrawn from the study because of lack of efficacy. Specifically, patients who experience treatment failure between Week 12 through Week 52 are eligible to receive rescue therapy with another immunosuppressive medication, IV Ig, plasmapheresis, rituximab, or another treatment or procedure as per the investigator's best medical judgment and continue to be followed in the 52-week treatment period per the treatment period schedule of assessments (see [Appendix 1](#)). Details of additional therapies for PV should be reported as concomitant medications.

If a patient receives rescue therapy with any medication, dose and dosing schedule will be at the discretion of the investigator. Every effort will be made to maintain the study blind, but the patient may be unblinded at the discretion of the Principal Investigator's safety assessment. Patients who receive rescue infusions with rituximab from Week 12 through Week 24 will not receive the scheduled rituximab or matching placebo infusions on Days 168 and 182. Careful consideration should also be given as to whether MMF/matching placebo are continued following rescue therapy with any immunosuppressive medication.

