Patients who receive rescue therapy will be evaluated up to the point of rescue only for all main efficacy analyses. Methods for data handling and/or imputing post-rescue data are described throughout Section 4.7. Additional exploratory summaries on key efficacy assessments will be produced that will include rescue data. Safety analyses will include data up to the point of rescue only.

Listings will include all data, including data post-rescue treatment.

Depending on the proportion of patients receiving rescue, patients will be analyzed separately using descriptive statistics for key analyses on study conduct, efficacy, and safety. For relevant summaries, patients may be re-baselined at the time of rescue and data presented as pre- and post-rescue treatment. Rescue analyses will use data as observed. Subject to patient counts, a limited number of analyses may be summarized by type of rescue received (MMF given as rescue, RTX given as rescue, or other).

Rituximab—F. Hoffmann-La Roche Ltd
12/Statistical Analysis Plan WA29330

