For reporting purposes, all relevant oral corticosteroid entries will be standardized by converting to a prednisone equivalent dose, and will be reported under the term 'Prednisone'. A listing of all compounds reported as prednisone will be produced along with the conversion factor applied.

The study management team will monitor oral corticosteroids on an ongoing basis for data quality and to ensure all dose adjustments are being correctly captured. All efforts

Rituximab—F. Hoffmann-La Roche Ltd
20/Statistical Analysis Plan WA29330

will be made to resolve missing or ambiguous data prior to database lock. In the case that data queries cannot be resolved, data will be handled in a conservative manner as described in the sections below.

The intervals for each dose of oral corticosteroid captured during the taper are expected to be continuous and non-overlapping. Patients who are adequately controlled by their blinded treatment may discontinue oral corticosteroids altogether, but may re-start treatment as required to treat any increases in disease activity. With this in mind, the use of available data will be maximized and incorporated into the imputation of missing or partial dates as follows:

Missing Term	Imputation Method
Start Date	
Missing Day	Latest of the following: Previous End Date+1 First day of the month
Missing Month	Previous End Date+1
Missing Year	No imputation
End Date	
Missing Day	Earliest of the following: Next Start Date-1 Last day of the month
Missing Month	Next Start Date-1
Missing Year	No imputation

Within two consecutive dosing intervals, if the end date of the first dose interval is missing and the start date of the second dose interval is missing, a midpoint approach using the start date of the first interval and the end date of the second interval will be used to assign a cut-off end date, providing these dates are available.

A missing or 'ongoing' final end date will be imputed with the exposure date. A missing initial start date will be imputed with Day 1 providing the end date is after Day 1, otherwise no imputation will be made.

If the total daily dose is missing then the dose will be imputed using the dose from the previous dose or the next dose, whichever is higher.

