4.7.2.2 Total Number of Flares

The total number of flares occurring during the treatment period will be evaluated by taking into account the number of flares experienced and the exposure period. Patient level flare and exposure data will then be aggregated, and the rate of flares compared between the RTX and MMF treatment groups. Rate of flare will be analyzed using a Poisson regression model with a log link and the log of each patient's duration in study as an offset variable. The model will include factors for treatment, region, duration of illness, baseline PDAI activity score, and baseline prednisone dose. The total number of flares, total exposure (weeks), and rate of flare will be presented by treatment group along with maximum likelihood estimates for the rate ratio, 95% confidence interval for the rate ratio, and p-value. A Pearson Chi-Square test will be used to assess over-dispersion of Poisson model. If an over-dispersion is detected based on this test, then a negative binomial model will be used. If the number of flares has an excess of zero counts according to the score test ([van den Broek, 1995](#)), a zero-inflated negative binomial model will be applied.

The exposure period for a patient will be the duration from Day 1 to the earliest of the following: early withdrawal, receipt of rescue, Week 52 visit.

Additional exploratory work may be undertaken to investigate the potential changes of flare rates over time, for example by assessing the number of flares over specified time intervals.

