4.10.4 Missing Data

Methods for handling missing data for efficacy analyses are described in detail throughout Section 4.7. Missing or partial dates for AEs, concomitant medications (except oral corticosteroids), laboratory assessments, and medical history will be imputed as detailed in [Appendix 11](#).

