Appendix 11 Imputation Rules for Partial or Missing Dates

	Start Date/Time	End Date/Time
Concomitant Medications	
Partially Missing Day: First day of the month (i.e., 01) Month: January Year: No imputation Seconds: 00 Minutes: 00 Hours: 00 Completely Missing Date: No imputation Time: 00:00:00 Note: if end time is available and start/end dates are equal and the imputed start time is after end time then impute start time with end time
	
Partially Missing Day: Last day of the month Month: December Year: No imputation Seconds: 59 Minutes: 59 Hours: 23 Completely Missing Date: No imputation Time: 23:59:59

Medical History	
Partially Missing Day: First day of the month (i.e., 01) Month: January Year: No imputation Seconds: 00 Minutes: 00 Hours: 00 Completely Missing Date: No imputation Time: 00:00:00 Note: if end time is available and start/end dates are equal and the imputed start time is after end time then impute start time with end time
	
Partially Missing Day: Last day of the month Month: December Year: No imputation Seconds: 00 Minutes: 00 Hours: 00 Completely Missing Date: No imputation Time: 00:00:00

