Appendix 11 Imputation Rules for Partial or Missing Dates (cont.)

	Start Date/Time	End Date/Time
Laboratory	Partially Missing Day: No imputation Month: No imputation Year: No imputation Seconds: 23 Minutes: 59 Hours: 59 Completely Missing Date: No imputation Time: 23:59:59	Partially Missing Day: No imputation Month: No imputation Year: No imputation Seconds: 23 Minutes: 59 Hours: 59 Completely Missing Date: No imputation Time: 23:59:59
Adverse Events	Partially Missing Day: If the MM-YYYY of start date is not equal to the MM-YYYY of first treatment date then set to 01-MM-YYYY. If the MM-YYYY of start date is equal to the MM-YYYY of first treatment date then if the end date is \geq date of first treatment set to max(01-MM-YYYY, date of first treatment) , otherwise if end date < date of first treatment set to 01-MM-YYYY. Month: Set to max(01-01-YYYY, date of first treatment). Year: Set to start date of first treatment. Seconds: 59 Minutes: 59 Hours: 23 Completely Missing Set to start date of first treatment. Note: For all imputations above, if the resulting imputed start date is after the end date then set start date to end date.	Partially Missing Day: Set to last day of the month, unless the outcome is death in which case impute with min(last day of month, date of death) Month: December, unless the outcome is death in which case impute with min(DD-12-YYYY, date of death) Year: If the outcome is death then impute with the date of death, otherwise no imputation. Seconds: 59 Minutes: 59 Hours: 23 Completely Missing If the outcome is death then impute with the date of death, otherwise no imputation.

**STATISTICAL ANALYSIS PLAN
48-WEEK SAFETY FOLLOW-UP**

TITLE: A RANDOMIZED, DOUBLE-BLIND, DOUBLE DUMMY, ACTIVE-COMPARATOR MULTICENTER STUDY TO EVALUATE THE EFFICACY AND SAFETY OF RITUXIMAB VERSUS MYCOPHENOLATE MOFETIL IN PATIENTS WITH PEMPHIGUS VULGARIS

PROTOCOL NUMBER: WA29330

STUDY DRUG: Rituximab

VERSION NUMBER: 1

IND NUMBER: 121595

EUDRACT NUMBER: 2014-000382-41

SPONSOR: F. Hoffmann-La Roche Ltd.

PLAN PREPARED BY: [REDACTED], Ph.D.

DATE FINAL: See electronic date stamp below.

STATISTICAL ANALYSIS PLAN APPROVAL

Date and Time(UTC)	Reason for Signing	Name
18-Oct-2019 13:14:46	Company Signatory	[REDACTED]

CONFIDENTIAL

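### A partial rescue start date falls by default under the concomitant-medication date rule, which takes the earliest possible date and has no lower bound

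*SAP*

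**What the plan says.** **Where rescue is recorded.** On rescue given from Week 12 to Week 52, Protocol 4.4.2 says: "Details of additional therapies for PV should be reported as concomitant medications". Protocol 4.4 treats added immunosuppressants and cell-depleting agents the same way: these "or other standard-of-care therapies per best medical judgment must be reported as concomitant medications".

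**Which date rule applies.** SAP 4.10.4 refers missing efficacy data to Section 4.7 and then states: "Missing or partial dates for AEs, concomitant medications (except oral corticosteroids), laboratory assessments, and medical history will be imputed as detailed in" Appendix 11. For the start of a concomitant medication, Appendix 11 reads "Day: First day of the month (i.e., 01) Month: January Year: No imputation". Section 4.7 has no rule for an incomplete rescue date.

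**What the rescue date controls.** SAP 4.2 makes starting rescue a treatment-failure event and adds: "Patients who receive rescue therapy will be evaluated up to the point of rescue only for all main efficacy analyses". SAP 4.7.1.4 drops data from the first failure event when responder status is set. In SAP 4.7.2.2, flare exposure is "the duration from Day 1 to the earliest of the following: early withdrawal, receipt of rescue, Week 52 visit", and its logarithm is the model offset. SAP 4.7.2.5 sets DLQI scores to missing after rescue. SAP 4.9 stops the main safety analyses at rescue.

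**How comparable dates are treated.** An adverse-event start with a missing month has a floor: "Month: Set to max(01-01-YYYY, date of first treatment"). An oral-corticosteroid start uses the neighbouring record: "Missing Month Previous End Date+1".

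**The concern.** The concomitant-medication rule always picks the earliest date compatible with what was recorded. That does little harm in a medication table. Here the same date decides how much of a patient's follow-up counts.

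Dating rescue too early has three possible effects:

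- It can undo the protection in SAP 4.2, under which a patient who reaches sustained complete remission before any failure event remains a responder whatever happens later.
- It can give a flare exposure of zero or less, in the second-ranked secondary endpoint.
- It can shift pre-rescue safety observations into the post-rescue summaries.

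The fallback in SAP 2.3, which makes a patient of undeterminable status a non-responder, does not come into play, because the rule does return a date.

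**Working it through.** **Design figure.** SAP 2.3 states about 80% power for 40% versus 65% with 61 per arm, two-sided 5%. With a chi-squared test without continuity correction, the standard error is √(2 × 0.525 × 0.475/61) = 0.0904 under the null and √((0.24 + 0.2275)/61) = 0.0875 under the alternative. Then z = (0.25 − 1.96 × 0.0904)/0.0875 = 0.83, which gives power 0.797. The figure is reproduced and is not in dispute. One changed responder moves an arm's rate by 1/61 = 1.6 percentage points.

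**Assumptions for the date check.** First dose falls on each of 365 calendar days with equal weight. The true rescue day is uniform over Day 84 (Week 12) to Day 364 (Week 52), which is 281 days. That gives 365 × 281 = 102,565 combinations.

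**Only the day missing (set to the 1st).**
- The shift is 0 to 30 days. Over a 365-day year the mean is (7 × 465 + 4 × 435 + 378)/365 = 5,373/365 = 14.7 days.
- The earliest possible result is Day 84 − 30 = Day 54, so no date precedes first dose. About 5% of combinations fall before Week 12.

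**Month missing, year known (set to 1 January).**
- The shift is 0 to 364 days, with mean (0 + … + 364)/365 = 182 days.
- The imputed date is on or before first dose whenever rescue falls in the same calendar year as first dose. For rescue k days after first dose (k = 83 to 363) that covers 365 − k first-dose days. The sum is 282 + … + 2 = 142 × 281, so the share is 142/365 = 38.9%. Without the case of a first dose on 1 January itself, it is 141/365 = 38.6% strictly before.
- Rescue in the following year is still dated before Day 84 if first dose fell in the last 82 days of the year. The total before Week 12 is (142 + 82)/365 = 224/365 = 61.4%.

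**Example A, flare exposure.** First dose is 1 March 2016 and true rescue 20 October 2016 (Day 234), with the month missing. The imputed date is 1 January 2016, which is 60 days before first dose. Exposure is negative, so its logarithm does not exist.

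**Example B, primary endpoint.** First dose is 1 September 2016 and true rescue 20 May 2017 (Day 262). On the guideline taper from 60 mg (Protocol Table 1), Steps 2 and 3 take 1 week each and Steps 4 to 11 take 2 weeks each: 1 + 1 + 8 × 2 = 18 weeks. So 0 mg can begin on Day 127, and 16 weeks can be complete on Day 126 + 112 = 238. With a PDAI activity score of 0 throughout, the patient is a responder before rescue.
- Month missing: imputed date 1 January 2017 (Day 123), a loss of 262 − 123 = 139 days. The patient becomes a non-responder.
- Only the day missing: imputed date 1 May 2017 (Day 243). The patient remains a responder.

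**Effect of a floor.** If the imputed date may not precede the last scheduled visit before the true rescue, no date falls before first dose. The shift is then at most 55 days (mean 19) with the month missing and at most 30 days (mean 10) with only the day missing. A floor at Week 12 alone would still allow up to 280 days (mean 104).

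**The case against.** The strongest reply is that the serious case needs a missing month. A site would have to know the year of an investigator-initiated rescue but not its month, although concomitant medications are reviewed at every scheduled visit. Protocol 7.1 provides for data queries and 7.4 for source verification. A rescue dated before Week 12 or before first dose would be conspicuous, and a negative exposure would stop the model visibly. This stands, and it limits how often the problem can arise.

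With only the day missing, status changes only when rescue follows completed remission within 30 days and the 1st of that month precedes completion. A rescued patient who had not completed 16 weeks is a non-responder on either date, and an earlier failure criterion may already have cut the data. This also stands.

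Appendix 11 does not name rescue, and the case report form is not in the documents, so a separately dated rescue field cannot be excluded. But neither document describes one, and 4.10.4 excepts only oral corticosteroids. The ongoing review of medication data in SAP 4.7.2.1 appears under the corticosteroid heading.

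A reader might infer that early dating removes all of the patient's data. It does not. Under SAP 4.2, listings keep everything and exploratory summaries include rescue data, and SAP 4.9 summarises post-rescue safety separately for selected outputs. A reader might also infer that a rescue dated before Day 1 would go unrecognised, so that later remission counts as response. That needs a rule identifying rescue by a start after Day 1, and the SAP has none.

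**Conclusion.** The gap is real and minor. Followed as written, the SAP dates a partially recorded rescue too early, while it bounds the comparable adverse-event and corticosteroid dates. A missing day costs at most 30 days and never reaches first dose. A missing month costs about 182 days on average, with about 39% of dates before first dose and about 61% before Week 12. These shares depend on the month being unknown and on the uniform-date assumptions.

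Primary status changes only for patients who completed 16 weeks of remission after the imputed date but before the true one, at 1.6 percentage points per patient. Safety data are moved to the post-rescue summaries rather than lost. The documents give no count of partial rescue dates, and the count is probably small. They therefore do not support a claim that the trial's conclusion or power is affected, or that the error favours a particular arm.

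**What to change.** Add a row to SAP Appendix 11, and a sentence in 4.10.4 pointing to it, for pemphigus rescue therapies. A partial start date becomes the latest of:

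- the first day of the recorded month (or year);
- the day after the last visit at which the patient was recorded as not on that therapy;
- the date of first dose.

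It must not be later than the recorded end date. State that a therapy flagged as rescue keeps the flag whatever date is imputed. If any partial rescue date remains at database lock, repeat the primary analysis with the latest compatible date.

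The cost is one appendix row and minor programming. No new data are needed, and sample size and power do not change. The rule should be settled before unblinding.

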4.11 INTERIM ANALYSES

No efficacy interim analyses are planned.

Appendix 1 Protocol Synopsis

PROTOCOL SYNOPSIS

TITLE: A RANDOMIZED, DOUBLE-BLIND, DOUBLE-DUMMY, ACTIVE-COMPARATOR, MULTICENTER STUDY TO EVALUATE THE EFFICACY AND SAFETY OF RITUXIMAB VERSUS MMF IN PATIENTS WITH PEMPHIGUS VULGARIS

PROTOCOL NUMBER: WA29330

VERSION NUMBER: 5

EUDRACT NUMBER: 2014-000382-41

IND NUMBER: 121595

TEST PRODUCT: Rituximab (RO 0452294)

PHASE: III

INDICATION: Moderate-to-severely active pemphigus vulgaris

SPONSOR: F. Hoffmann-La Roche Ltd

Objectives

Efficacy Objectives

The primary efficacy objective for this study is as follows:

- To evaluate the efficacy of rituximab compared with mycophenolate mofetil (MMF) in achieving sustained complete remission, evaluated by the Pemphigus Disease Area Index (PDAI; see Section 3.4.1.1), and assessed at Week 52 in patients with moderate-to-severely active pemphigus vulgaris (PV)

The secondary efficacy objectives for this study are as follows:

- To evaluate the efficacy of rituximab compared with MMF, as measured by the time to disease flare, the duration of sustained complete remission, the total number of disease flares during the treatment period, and the time to initial sustained complete remission
- To assess corticosteroid exposure over 52 weeks
- To assess the effect of rituximab compared with MMF on health-related quality of life (HRQoL), as measured by the Dermatology Life Quality Index (DLQI)
- To assess the effect of rituximab compared with MMF on patients' impression of PV symptoms, as measured by the Patient Global Impression of Change (PGIC) questionnaire
- To assess the effect of rituximab compared with MMF on clinician impression of patients' PV symptoms, as measured by the Clinician Global Impression of Change (CGIC) questionnaire

Safety Objectives

The safety objectives for this study are as follows:

- To evaluate the safety of rituximab compared with MMF, with a focus on AEs and safety laboratory values
- To evaluate corticosteroid-related AEs in relation to corticosteroid exposure

Rituximab—F. Hoffmann-La Roche Ltd
37/Statistical Analysis Plan WA29330

Appendix 1 Protocol Synopsis (cont.)

Exploratory Objectives

The exploratory objectives for this study will include, but are not limited to, the following:

- To evaluate the efficacy of rituximab compared with MMF, as measured by the proportion of patients achieving complete or partial remission by 24 weeks and 52 weeks
- To explore the pharmacokinetics and pharmacodynamics of rituximab, and the pharmacodynamics of MMF, in patients with PV
- To evaluate the effect of rituximab as compared with MMF on the change in PDAI activity score
- To evaluate the effect of rituximab as compared with MMF on anti-desmoglein (anti-Dsg) autoantibody titers (anti-Dsg1 and anti-Dsg3) and other mechanistic studies of interest in patients with PV
- To assess the effect of rituximab compared with MMF on health utilities as measured by the European Quality of Life (EuroQol) 5-Dimension Questionnaire, 3-level version (EQ-5D-3L)
- To assess the effect of rituximab compared with MMF on HRQoL, as measured by the Skindex-29
- To evaluate the efficacy of rituximab compared with MMF, as measured by the proportion of patients experiencing treatment failure from Week 12 to Week 52

Study Design

Description of Study

This is a Phase III, randomized, double-blind, double-dummy, active-comparator, parallel-arm, multicenter study to evaluate the efficacy and safety of rituximab compared with MMF in patients with moderate-to-severely active PV requiring 60–120 mg/day oral (PO) prednisone or equivalent (1.0-1.5 mg/kg/day). Patients must have a confirmed diagnosis of PV within the previous 24 months (by skin or mucosal biopsy and immunohistochemistry) and evidence of moderate-to-severely active disease at screening (defined as at total PDAI activity score of ≥ 15).

This international study will be conducted at investigational sites throughout North America, Europe, the Middle East, and Latin America. It is expected that approximately 60 centers will participate. Approximately 132 patients will be randomized in a 1:1 ratio to receive either rituximab plus MMF placebo or rituximab placebo plus MMF. Randomization will be stratified by duration of illness (newly diagnosed [i.e., diagnosed within the 1 year prior to screening] vs. diagnosed greater than 1 year) and geographical region (North America [U.S./Canada] vs. rest of world).

The study will consist of three periods: a screening period of up to 28 days, a 52-week double-blind treatment period, and a 48-week safety follow-up (SFU) period that begins at the time of study treatment completion or discontinuation.

Rituximab (1000 mg or matching placebo) will be administered by intravenous (IV) infusion on Day 1 and Day 15, with repeat rituximab (or matching placebo) administration on Day 168 and Day 182 provided specific safety criteria have been met (see Section 4.6.4). MMF (500 mg or matching placebo) will be administered PO twice daily (every 12 hours [Q12H]), starting with a total dose of 1 g/day on Day 1. The MMF dose will be titrated to achieve a goal of 2 g/day in divided doses (1 g Q12H) by Week 2. Treatment with MMF (or matching placebo) will continue through Week 52.

All patients who withdraw from the treatment period or who complete the total 52-week treatment period must return for post Week 52 SFU assessments at 12, 24, 36, and 48 weeks after either the early withdrawal visit or study treatment completion, respectively. Thus, patients will be followed for approximately 1 year in the SFU period.

Rituximab—F. Hoffmann-La Roche Ltd
38/Statistical Analysis Plan WA29330

